5.8. Safety Analysis

The primary safety objective of the study is to evaluate the safety and tolerability of ADG20 compared to placebo through Day 29 in participants with mild or moderate COVID-19 and high risk of disease progression. A secondary objective is to evaluate safety through Month 14. Safety assessments will include monitoring of AEs, clinical laboratory testing, and vital sign measurements.

5.8.1. Adverse Events

5.8.1.1. Unsolicited Adverse Events

An AE is defined as any untoward medical occurrence in a participant enrolled into this study regardless of its causal relationship to the study drug. AEs occurring from when the participant signs the ICF until the Month 14 (EOS) visit or discontinuation from study will be recorded. Only study procedure-related AEs occurring before randomization will be recorded. AEs resulting from concurrent illnesses, reactions to concurrent illnesses, reactions to concurrent medications, or progression of disease states must also be reported. Exceptions to this reporting related to COVID-19 signs and symptoms are described in the protocol (Section 6.4.6.3.2). All AEs will be followed to adequate resolution. MedDRA version 24 or higher will be used to code all AEs.

5.8.1.2. Injection Site Reactions

Intramuscular ISRs will be recorded in the Injection Site Reaction Diary (refer to the protocol, Appendix 12.3) and graded using the FDA Guidance for Industry: Toxicity Grading Scale for Healthy Adult and Adolescent Volunteers Enrolled in Preventive Vaccine Clinical Trials ([FDA 2007](#)).

Participants will be instructed to record the worst severity ([Table 5](#)) experienced during each recording period (prior 24 hours) of the following local (solicited) AEs through Day 4, and whether medication was taken to relieve the symptoms:

- Injection site pain or tenderness
- Erythema/redness at the site of injection
- Induration/swelling at the site of injection

Table 5: Grading of Injection Site Reactions

Local Reaction to Injectable Product	Grade 1 Mild	Grade 2 Moderate	Grade 3 Severe	Grade 4 Potentially Life-Threatening ^a
Pain	Does not interfere with activity	Repeated use of non-narcotic pain reliever >24 hours or interferes with activity	Any use of narcotic pain reliever or prevents daily activity	ER visit or hospitalization
Tenderness	Mild discomfort to touch	Discomfort with movement	Significant discomfort at rest	ER visit or hospitalization
Erythema/redness	2.5–5 cm	5.1–10 cm	>10 cm	Necrosis or exfoliative dermatitis
Induration/ Swelling ^b	2.5–5 cm and does not interfere with activity	5.1–10 cm or interferes with activity	>10 cm or prevents daily activity	Necrosis

ER=emergency room.

Note: In addition to grading the measured local reaction at the greatest single diameter, the measurement should be recorded as a continuous variable.

^a Pain/tenderness are not expected to be life-threatening but can still meet Grade 4 criteria based on ER visit or hospitalization.

^b Induration/swelling should be evaluated and graded using the functional scale as well as the actual measurement.

Erythema/redness and induration/swelling reported as <2.5 cm in greatest diameter will be classified as *Non-Graded*.

For summaries combining ISRs and other AEs, ISRs will be mapped to MedDRA SOC and PT as shown in [Table 6](#).

Table 6: Injection Site Reaction Mapping to MedDRA Coding

Injection Site Reaction Term	System Organ Class	Preferred Term
Pain	General disorders and administration site conditions	Injection site pain
Tenderness	General disorders and administration site conditions	Injection site pain
Erythema	General disorders and administration site conditions	Injection site erythema
Redness	General disorders and administration site conditions	Injection site erythema
Induration	General disorders and administration site conditions	Injection site induration
Swelling	General disorders and administration site conditions	Injection site swelling
Necrosis	General disorders and Administration site conditions	Injection site necrosis
Exfoliative dermatitis	Skin and subcutaneous tissue disorders	Dermatitis exfoliative

An ISR that is reported on multiple days will be considered one ISR with the start date defined as the date the ISR was first reported and with an end date defined as the date the ISR is reported as not occurring (ie, none) in the diary or the date of resolution for the ISR Resolution eCRF. Maximum severity will be assigned.

5.8.1.3. Treatment Emergent Adverse Events

A TEAE is defined as any AE that has an onset during or after the administration of study drug through the Month 14 visit, or any preexisting condition that has worsened during or after the administration of study drug through the Month 14 Visit. Because solicited AEs (ISRs in participants receiving IM injection) are expected to occur after the administration of study drug, all solicited AEs will be considered study drug related TEAEs.

5.8.1.4. Adverse Events of Special Interest

An AESI, which can be serious or nonserious, is defined as an AE or SAE of scientific and medical concern specific to the sponsor's product or program, for which ongoing monitoring and rapid communication by the investigator to the sponsor or designee could be appropriate (ICH E2F; CIOMS VI).

For this study, AESIs are specified in the protocol as follows: Hypersensitivity reactions occurring through Day 4. Hypersensitivity reactions include but are not limited to anaphylaxis, anaphylactic shock, bronchospasm, hypotension, loss of consciousness, generalized skin rash, angioedema, bronchoconstriction, allergic bronchial asthma, allergic rhinitis, allergic

conjunctivitis, drug allergy, immune thrombocytopenia, autoimmune hemolytic anemia, rash, urticaria, arthus reaction, etc.

Determination of hypersensitivity reactions will be based on a sponsor medical adjudication based on the narrow and broad terms of the 3 SMQs hypersensitivity, anaphylactic reaction, and angioedema.

All hypersensitivity reactions will be summarized through Day 4, through Day 29, and through Month 14/EOS. However, only those reactions occurring through Day 4 will be considered AESIs.

5.8.1.5. Medically Attended Adverse Events

MAAEs are defined as AEs leading to medically attended visits that are not routine visits for physical examination or vaccination, such as an emergency room visit, or an otherwise unscheduled visit to or from medical personnel (medical doctor) for any reason other than the illness under study (COVID-19). AEs, including abnormal vital signs, identified on a routine study visit or during the scheduled illness visits will not be considered MAAEs.

5.8.1.6. Serious Adverse Events

An SAE is defined as any event that:

- results in death
- is immediately life-threatening
- requires inpatient hospitalization or prolongation of existing hospitalization
- results in persistent or significant disability/incapacity
- is a congenital anomaly/birth defect

5.8.1.7. Severity

The severity, or intensity, of an AE refers to the extent to which an AE affects the participant's daily activities. The intensity of all unsolicited AEs will be graded by the investigator according to the DAIDS Table for Grading the Severity of Adult and Pediatric Adverse Events ([NIAID 2017](#)). The DAIDS grading table provides an AE severity grading scale ranging from grades 1 to 5 with descriptions for each AE based on the following general guidelines:

- Grade 1 indicates a mild event
- Grade 2 indicates a moderate event
- Grade 3 indicates a severe event
- Grade 4 indicates a potentially life-threatening event
- Grade 5 indicates death (Note: This grade is not specifically listed on each page of the grading table.)

Missing severity is not imputed.

Grading criteria for ISRs are provided in Section [5.8.1.2](#).

5.8.1.8. Relationship of Adverse Events to Study Drug

The investigator will assess causality (ie, whether there is a reasonable possibility that the study drug caused the event) for all unsolicited AEs. The relationship will be characterized using the following classification:

- Not related:

There is not a reasonable possibility of a relationship to the study drug. The participant did not receive the study drug, temporal sequence of the AE onset relative to administration of the study drug is not reasonable, OR the AE is more likely explained by another cause than the study drug.

- Related:

There is a reasonable possibility of a relationship to the study drug. There is evidence of exposure to the study drug. The temporal sequence of the AE onset relative to the administration of the study drug is reasonable. The AE is more likely explained by the study drug than by another cause.

If relatedness is missing for an event, the event will be categorized as Related.

All ISRs are considered related to study drug.

5.8.1.9. Analysis of Adverse Events and Injection Site Reactions

All AE and ISR analyses will be performed using the Safety Set. For all analyses of AEs/ISR, if the same AE/ISR (based on PT) is reported for the same participant more than once, the AE/ISR is counted only once for the PT and at the highest severity and by relationship to study drug.

Percentages will be calculated based on the number of participants in each treatment group in the Safety Set. Missing and incomplete dates of AEs will be imputed as described in [Appendix D](#). In addition to safety summaries, listings of AEs (with TEAE designated by *), SAEs, and ISRs will be presented.

Safety summaries will be presented through Day 29 and overall. All summaries will be sorted by decreasing frequency of SOC/PT in the ADG20 arm. The AE/ISR summaries listed below will be provided:

- Overall summary of AEs (solicited and unsolicited) including the number/percentage of participants with:
 - a pre-treatment AE
 - a TEAE (and separately for unsolicited and solicited TEAEs)
 - a study drug related TEAE
 - \geq Grade 3 TEAE
 - an SAE
 - a study drug related SAE
 - a TEAE leading to death

- a study drug related TEAE leading to death
- a TEAE leading to treatment discontinuation
- an MAAE
- any hypersensitivity reaction (and separately for any hypersensitivity reaction through Day 4 [AESI])
- Incidence of TEAEs (including solicited ISRs) by SOC, PT, and treatment group
- Incidence of TEAEs (including solicited ISRs) occurring in >2% of participants in either arm by PT sorted by descending frequency of PT in the ADG20 arm
- Incidence of MAAE by SOC, PT, and treatment group
- Incidence of study drug related TEAEs (including solicited ISRs) by SOC, PT, and treatment group.
- Incidence of TEAEs (including solicited ISRs) by maximum severity by SOC, PT and treatment group
- Incidence of study drug related TEAEs (including solicited ISRs) by maximum severity by SOC, PT, and treatment group
- Incidence of solicited AEs (ISRs) and by maximum severity based on the FDA toxicity scale through Day 4 (only for Day 29 analysis)
- Incidence of SAEs by SOC, PT, and treatment group
- Incidence of SAEs excluding COVID-19 SAEs associated with the primary endpoint by SOC, PT, and treatment group; COVID-19-related PTs include COVID-19, COVID-19 pneumonia.
- Incidence of study drug related SAEs by SOC, PT, and treatment group
- For the Day 29 analysis only: incidence of solicited AEs (ISRs) summarized by maximum duration (defined as the end date-start date +1) of 1, 2, 3, 4, and >4 days for participants with any ISR and for each ISR type. Time from injection to report of first onset of any solicited ISR (in days) will also be summarized.
- Overall summary of hypersensitivity reactions including number and percentage of participants with:
 - any hypersensitivity reaction
 - a study drug related hypersensitivity reaction
 - a severe (\geq Grade 3) hypersensitivity reaction
 - a serious hypersensitivity reaction
 - any hypersensitivity reaction by onset day category of first reaction (Day 1, 2, 3, 4, 5-8, 9-14, 15-21, 22-29, >29). Time from study drug administration to first onset of

hypersensitivity reaction and the duration of the hypersensitivity reaction for participants with hypersensitivity reactions (longest duration if multiple) will also be summarized.

- Incidence of hypersensitivity reactions by SOC, PT, and treatment group through Day 4, through Day 29, and through Month 14/EOS.
- Incidence of hypersensitivity reactions by SOC, PT, maximum severity, and treatment group, through Day 4, through Day 29, and through Month 14/EOS.
- Overall summary of AEs and the incidence of AEs (including solicited ISRs) by SOC and PT, by age group (12-17, 18-65, >65 years).

A listing will be provided of participants meeting any pausing guideline in the ADG20 arm, as described in [Table 7](#).

Table 7: Study Pausing Guidelines

Phase	Pausing Guideline
Phase 2	
• 2 or more participants with a study drug-related \geqGrade 3 hypersensitivity reaction• 2 or more participants with a \geqGrade 3 injection site reaction• Any study drug-related death• Any study drug-related SAE, including hypersensitivity reactions
Phase 3	
• Any study drug-related death• Any study drug-related SAE, including hypersensitivity reactions

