6.4.1.2. Injection Site Reaction Diary

Solicited ISRs will be collected in the Injection Site Reaction (ISR) Diary from Day 1 through Day 4. Investigators or medically qualified designees will follow all ISRs that are ongoing beyond Day 4 to resolution. Each day, participants should document the worst pain, tenderness, redness, or swelling that was experienced in the last 24 hours. Participants will be provided a ruler by the site study team to measure redness or swelling at the injection sites. For irregular shapes, the widest part of the area (how much of the skin the redness or swelling covers) should be measured. Redness or swelling should be measured each day that it is visible. Severity will be assessed for solicited AEs (ISRs) by the participant (or, if applicable, with help from their caregiver, surrogate, or guardian/LAR) as described in Appendix [12.3](#).

At the Day 1 visit, study site staff will provide information to the participant (or guardian/LAR) about the questions that will be asked in the diary and how to complete the ISR Diary and use the measuring device. At the end of the post-dose monitoring period at the site, participants will complete the Day 1 ISR prior to departing the clinical site. Site staff will observe the participants completing the diary on Day 1 and will answer any questions participants may have about the diary.

Only ISRs that qualify as an SAE or that worsen or begin after Day 4 should be recorded in the eCRF AE form, all other ISRs are only to be recorded in the eDiary.

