7.11. Safety Analyses

All AEs will be coded using the latest version of MedDRA. Safety summaries will be presented through Day 29 and overall.

A TEAE is defined as any AE that has an onset during or after the administration of study drug through the Month 14 visit, or any preexisting condition that has worsened during or after the administration of study drug through the Month 14 Visit. Because solicited AEs are expected to occur after the administration of study drug all solicited AEs will be considered TEAEs.

The incidence of TEAEs (including solicited ISRs), SAEs, TEAEs related to study drug, SAEs related to study drug, TEAEs leading to study drug discontinuation, AESIs, and MAAEs will be summarized by MedDRA SOC, PT, and treatment group. The incidence of study drug related TEAEs (including solicited ISRs) will also be summarized by maximum severity by SOC, PT, and treatment group.

The incidence of solicited AEs (ISRs) will be summarized by maximum severity through Day 4. The maximum duration and time from injection to report of first onset of any solicited ISR will also be summarized.

For all analyses of AEs, if the same AE (based on PT) is reported for the same participant more than once, the AE is counted only once for the PT and at the highest severity and most-related relationship to study drug.

Descriptive statistics for clinical laboratory test results (hematology, serum chemistry, and coagulation) and vital signs will be presented by treatment group and time point assessed. Descriptive statistics for the change from baseline to each post-baseline time point for the laboratory and vital sign parameters will be summarized by treatment group. In addition, treatment-emergent potentially clinically significant (PCS) laboratory parameters will be summarized in shift tables from baseline to each post-baseline time point assessed. The number and percentage of participants with a PCS vital sign will be summarized by treatment group for each time point assessed. PCS values will be defined in the SAP.

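### The injection site reaction (ISR) duration formula adds 1 to a diary end date that is already reaction-free, so multi-day reactions closed in the diary are tabulated one day too long

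*SAP*

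**What the plan says.** Protocol 7.11 commits to the summary without giving a formula: "The maximum duration and time from injection to report of first onset of any solicited ISR will also be summarized".

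SAP 5.8.1.2 supplies the dates. It opens with "An ISR that is reported on multiple days will be considered one ISR", then sets "the start date defined as the date the ISR was first reported" and "an end date defined as the date the ISR is reported as not occurring (ie, none) in the diary". The alternative end date is "or the date of resolution for the ISR Resolution eCRF". The section does not say whether that resolution date is the last day with the reaction or the first day without it. It also gives no separate rule for an ISR reported on one day only.

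SAP 5.8.1.9 then defines the table, for the Day 29 analysis only, by "maximum duration (defined as the end date-start date +1) of 1, 2, 3, 4, and >4 days", for any ISR and for each ISR type.

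The diary runs from Day 1 to Day 4, and reactions still present after Day 4 are followed to resolution (Protocol 6.4.1.2). On recall, the protocol states: "Each day, participants should document the worst pain, tenderness, redness, or swelling that was experienced in the last 24 hours".

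**The concern.** End minus start plus 1 counts days inclusively, so both dates must be days on which the reaction was present. The diary end date in SAP 5.8.1.2 is instead the day on which the participant first records no reaction. Used together, the two definitions add a reaction-free day to the count. Nothing elsewhere in the protocol or SAP corrects this.

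At stake is the accuracy of the table describing how long injection site reactions last. The diary covers only four days and the table has five categories, so an error of one day moves a reaction into the wrong row.

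**Working it through.** The documents give no duration figure to reproduce, so the check is an enumeration.

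**Inputs.** Start date *s* is the first diary date reported, and end date *e* is the date of the diary 'none' (both SAP 5.8.1.2). The formula is *e* − *s* + 1 (SAP 5.8.1.9). The diary covers Days 1 to 4 (Protocol 6.4.1.2). Let *l* be the last diary date on which the ISR is reported. I assume complete diaries and uninterrupted reports, so *e* = *l* + 1.

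**Formula.** Days reported = *l* − *s* + 1. SAP duration = (*l* + 1) − *s* + 1 = *l* − *s* + 2. The difference is always 1.

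**All episodes that a diary 'none' can close by Day 4, with the end-date rule applied to every ISR:**

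| First reported | Last reported | First 'none' | Days reported | SAP duration |
|---|---|---|---|---|
| 1 | 1 | 2 | 1 | 2 − 1 + 1 = 2 |
| 1 | 2 | 3 | 2 | 3 − 1 + 1 = 3 |
| 1 | 3 | 4 | 3 | 4 − 1 + 1 = 4 |
| 2 | 2 | 3 | 1 | 3 − 2 + 1 = 2 |
| 2 | 3 | 4 | 2 | 4 − 2 + 1 = 3 |
| 3 | 3 | 4 | 1 | 4 − 3 + 1 = 2 |

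**Two readings for one-day ISRs.**

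- If the end-date rule also covers them, diary-closed durations can only be 2, 3 or 4, and no diary-closed ISR falls in the 1-day row.
- If one-day ISRs take end = start, diary-closed durations can only be 1, 3 or 4, and no diary-closed ISR falls in the 2-day row.

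The multi-day rows are one day too long on both readings. The excess is 1/2 = 50% for two-day reactions and 1/3 = 33% for three-day reactions.

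**eCRF route.** A reaction still present on Day 4 takes its resolution date *R* from the eCRF. If it was first reported on Day 4 and resolved on Day 5, the duration is 5 − 4 + 1 = 2, so this route can fill the 2-day row. If *R* is the last day with the reaction, the +1 is correct here, and the table then mixes two conventions. If *R* is the first day without it, a reaction present on Days 1 to 4 and resolved on Day 5 gets 5 − 1 + 1 = 5 and moves from the 4-day row to the >4 row.

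**After the fix.** With the end date set to *l* and the +1 kept, the six episodes give 1, 2, 3, 1, 2 and 1 days, equal to the days reported.

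**The case against.** The strongest reply is that diary recall also makes the start date late. The Day 1 entry is completed before the participant leaves the site (Protocol 6.2 and 6.4.1.2), after post-dose monitoring that was 4 hours at first and later 2 and then 1 (Table 6-1). A reaction that begins at home later on Day 1 is therefore first reported on Day 2. For any first report on day *s* ≥ 2, the reaction may have touched calendar days *s* − 1 to *e* − 1. That is *e* − *s* + 1 days, exactly the SAP value. For example, with onset on Day 1 evening, gone by Day 2 morning, reported on Day 2 and 'none' on Day 3, the SAP gives 3 − 2 + 1 = 2, and two calendar days were touched.

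This part stands. A reader might infer that, because each entry looks back 24 hours, the true overstatement exceeds one day. The documents do not support that for reactions first reported after Day 1.

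The reply does not rescue the rule, for two reasons. SAP 5.8.1.2 dates the start by the first report, so the table counts report days, and on that basis the extra day is an error. For reactions first reported on Day 1, even the calendar-day count is at most *e* − 1, while the SAP gives *e*.

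It is also fair to say that the table is descriptive, that both arms use the same rule, and that the error lengthens durations rather than hiding them. All of that is accepted and limits the weight of the point.

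**Conclusion.** The point holds for multi-day ISRs closed by a diary 'none': each is tabulated one day longer than the days on which it was reported (2 becomes 3, 3 becomes 4). This rests on the SAP's own definitions and on uninterrupted, complete diary entries.

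Three stronger readings are tempting, and the documents do not support them:

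- *Every diary-closed reaction moves up a row.* SAP 5.8.1.2 words its rule for reactions reported on several days, so one-day ISRs may be unaffected.
- *One particular row of the table can never be filled.* Which row diary-closed ISRs miss depends on how one-day ISRs are read. If it is the 2-day row, the eCRF route can still fill it.
- *The primary safety endpoint or the overall tolerability result is wrong.* The listed endpoint is the incidence of solicited ISRs through Day 4. Duration is a supporting summary for the Day 29 analysis. Incidence, maximum severity, the pausing guidelines and efficacy do not use it.

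What remains is a definite but small derivation error in one descriptive safety table. It should be corrected because the table would otherwise show wrong durations and the correction costs almost nothing.

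**What to change.** In SAP 5.8.1.2, define the end date of a diary-closed ISR as the last diary date on which it was reported. State that this includes one-day ISRs, for which end equals start. Keep the +1 in SAP 5.8.1.9.

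State also that the ISR Resolution eCRF date is handled on the same last-day-present basis. If the form records the first reaction-free day, the derivation should step back one day before the formula is applied.

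Simply dropping the +1 is less safe. On the eCRF route, a resolution date equal to the start date would then give 0 days, and the table has no such row.

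The cost is one sentence in the SAP and a matching line of derivation code. No new data are needed. SAP 3.2 has the SAP signed before unblinding, so the change can be made while the team is still blinded.
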